10.4.2 Statistical hypothesis, model, and method of analysis

10.4.2.1 Phase Ib

An adaptive BLRM guided by the EWOC principle will guide the dose escalation of the combination treatment to its MTD(s)/RP2D(s). A 5-parameter BLRM for combination treatment will be fitted on the dose-limiting toxicity data (i.e. absence or presence of DLT) accumulated throughout the dose escalation, for modeling the dose-DLT relationship of LGX818 (capsule formulation) and MEK162 when given in combination. While developing dual combination (LGX818 and MEK162) all information available about the dose-DLT relationship of the single agents LGX818 (i.e., from [LGX818X2101] study on both the capsule and micro-emulsion formulations) and MEK162 [ARRAY-162-111 study] will be summarized in prior distributions, based on a meta-analytical predictive approach to properly down-weight the information. The 5 parameter BLRM will be extended to a 10-parameter BLRM to model the dose-DLT relationship of LGX818 (capsule formulation) and MEK162 and LEE011 when given in combination. Three week on 1 week off DLT data from [CLEE011X2101] will be summarized in prior distributions based on a meta-analytical predictive approach to properly down-weight the information.

The 5-parameter BLRM for MEK162 original tablet

The 5-parameter BLRM is formulated in the following way: Let $\pi_1(d_1)$ be the probability of a DLT if LGX818 is given as a single agent at dose d_1 , and $\pi_2(d_2)$ the probability of a DLT if MEK162 is given as a single agent at dose d_2 . The dose-response relationship is then modeled as:

$$\text{LGX818: } \text{logit}(\pi_1(d_1)) = \log(\alpha_1) + \beta_1 \log(d_1/d_1^*)$$

$$\text{MEK162 original tablet: } \text{logit}(\pi_2(d_2)) = \log(\alpha_2) + \beta_2 \log(d_2/d_2^*)$$

$$\begin{aligned} \text{Odds}(\pi_{12}(d_1, d_2)) &= \pi_{12}(d_1, d_2) / (1 - \pi_{12}(d_1, d_2)) \\ &= \exp(\eta_{12}(d_1/d_1^*)(d_2/d_2^*)) (\pi_1(d_1) + \pi_2(d_2) - \pi_1(d_1)\pi_2(d_2)) / ((1 - \pi_1(d_1))(1 - \pi_2(d_2))), \end{aligned}$$

where

- $\text{logit}(\pi(d)) = \log[\pi(d) / \{1 - \pi(d)\}]$, $\pi(d)$ is the probability of a DLT at dose d ,
- $\pi_{12}(d_1, d_2)$ is the probability of a DLT given the combination doses
- $d_1^* = 100\text{mg}$ and $d_2^* = 60\text{mg}$ are the reference doses of LGX818 and MEK162 original tablet respectively,
- $\alpha_1, \alpha_2, \beta_1, \beta_2 > 0$ and $-\infty < \eta_{12} < \infty$ is a scalar. With η_{12} the interaction term between LGX818 and MEK162 original tablet.

For further details on the statistical model including the prior specification for the model parameters refer to [Appendix 5](#).

The 5-parameter BLRM for MEK162 smaller tablet/ new tablet variant

The 5-parameter BLRM is formulated in the following way: Let $\pi_1(d_1)$ be the probability of a DLT if LGX818 is given as a single agent at dose d_1 , and $\pi_3(d_3)$ the probability of a DLT if

MEK162 is given as a single agent at dose d_3 . The dose-response relationship is then modeled as:

$$\text{LGX818: } \text{logit}(\pi_1(d_1)) = \log(\alpha_1) + \beta_1 \log(d_1/d_1^*)$$

$$\text{MEK162 smaller tablet/ new tablet variant: } \text{logit}(\pi_3(d_3)) = \log(\alpha_3) + \beta_3 \log(d_3/d_3^*)$$

$$\begin{aligned} \text{Odds}(\pi_{13}(d_1, d_3)) &= \pi_{13}(d_1, d_3) / (1 - \pi_{13}(d_1, d_3)) \\ &= \exp(\eta_{13}(d_1/d_1^*)(d_3/d_3^*)) (\pi_1(d_1) + \pi_3(d_3) - \pi_1(d_1)\pi_3(d_3)) / ((1 - \pi_1(d_1))(1 - \pi_3(d_3))), \end{aligned}$$

where

- $\text{logit}(\pi(d)) = \log[\pi(d) / \{1 - \pi(d)\}]$, $\pi(d)$ is the probability of a DLT at dose d ,
- $\pi_{13}(d_1, d_3)$ is the probability of a DLT given the combination doses
- $d_1^* = 100\text{mg}$ and d_3^* are the reference doses of LGX818 and MEK162 respectively. The value of d_3^* will be determined prior to first DETC for the MEK162 smaller tablet/ new tablet variant.
- $\alpha_1, \alpha_3, \beta_1, \beta_3 > 0$ and $-\infty < \eta^{13} < \infty$ is a scalar. With η^{13} the interaction term between LGX818 and MEK162 smaller tablet/new tablet variant.

For further details on the statistical model including the prior specification for the model parameters refer to Appendix 5.

The 10-parameter BLRM

The 10-parameter BLRM is formulated in the following way: Let $\lambda_1(d_1)$ be the probability of DLT if LGX818 is given as a single agent at QD dose d_1 , $\lambda_2(d_2)$ the probability of DLT if MEK162 is given as a single agent at BID dose d_2 , and $\lambda_3(d_3)$ the probability of DLT if LEE011 is given as a single agent at 3 week on 1 week off dose of d_3 .

The single agent dose-DLT relationships are then modeled as:

$$\text{LGX818: } \text{logit}(\pi_1(d_1)) = \log(\alpha_1) + \beta_1 \log(d_1/d_1^*)$$

$$\text{MEK162: } \text{logit}(\pi_2(d_2)) = \log(\alpha_2) + \beta_2 \log(d_2/d_2^*)$$

$$\text{LEE011: } \text{logit}(\pi_4(d_4)) = \log(\alpha_4) + \beta_3 \log(d_4/d_4^*)$$

The dose-DLT relationships of the dual combinations of LGX818+MEK162, LGX818+LEE011 and MEK162+LEE011 are modeled as:

$$\begin{aligned} \text{Odds}(\pi_{12}(d_1, d_2)) &= \pi_{12}(d_1, d_2) / (1 - \pi_{12}(d_1, d_2)) \\ &= \exp(\eta_{12}(d_1/d_1^*)(d_2/d_2^*)) (\pi_1(d_1) + \pi_2(d_2) - \pi_1(d_1)\pi_2(d_2)) / ((1 - \pi_1(d_1))(1 - \pi_2(d_2))), \end{aligned}$$

$$\begin{aligned} \text{Odds}(\pi_{14}(d_1, d_4)) &= \pi_{14}(d_1, d_4) / (1 - \pi_{14}(d_1, d_4)) \\ &= \exp(\eta_{14}(d_1/d_1^*)(d_4/d_4^*)) (\pi_1(d_1) + \pi_4(d_4) - \pi_1(d_1)\pi_4(d_4)) / ((1 - \pi_1(d_1))(1 - \pi_4(d_4))), \end{aligned}$$

$$\begin{aligned} \text{Odds}(\pi_{24}(d_2, d_4)) &= \pi_{24}(d_2, d_4) / (1 - \pi_{24}(d_2, d_4)) \\ &= \exp(\eta_{24}(d_4/d_4^*)(d_2/d_2^*)) (\pi_2(d_2) + \pi_4(d_4) - \pi_2(d_2)\pi_4(d_4)) / ((1 - \pi_2(d_2))(1 - \pi_4(d_4))), \end{aligned}$$

The dose-DLT relationship of the triple combination is subsequently modeled as:

$$\text{Odds}(\pi_{124}(d_1, d_2, d_4)) = \pi_{124}(d_1, d_2, d_4) / (1 - \pi_{124}(d_1, d_2, d_4))$$

$$= \frac{\exp(\eta_{124}(d_1/d_1^*)(d_2/d_2^*)(d_4/d_4^*) + \eta_{12}(d_1/d_1^*)(d_2/d_2^*) + \eta_{14}(d_1/d_1^*)(d_4/d_4^*) + \eta_{24}(d_2/d_2^*)(d_4/d_4^*))(\pi_1(d_1) + \pi_2(d_2) + \pi_4(d_4) - \pi_1(d_1)\pi_2(d_2) - \pi_1(d_1)\pi_4(d_4) - \pi_2(d_2)\pi_4(d_4) + \pi_1(d_1)\pi_2(d_2)\pi_4(d_4))}{((1 - \pi_1(d_1))(1 - \pi_2(d_2))(1 - \pi_4(d_4)))}$$

where $\text{logit}(\pi.(d.)) = \log[\pi.(d.)/\{1 - \pi.(d.)\}]$, $d_1^* = 100\text{mg (QD)}$, $d_2^* = 60\text{mg (BID)}$ and $d_4^* = 400\text{mg (3 week on 1 week off)}$ are the reference doses of LGX818, MEK162 and LEE011 respectively, $\alpha_1, \alpha_2, \alpha_4, \beta_1, \beta_2, \beta_4 > 0$ and $-\infty < \zeta_{12}, \zeta_{13}, \zeta_{23}, \zeta_{124} < \infty$ are constants.

For further details on the statistical model including the prior specification for the model parameters refer to [Appendix 6](#).

Dose recommendation

Dose recommendation will be based on posterior summaries including the mean, median, standard deviation, 95%- credible interval, and the probability that the true DLT rate for each dose combination lies in one of the following categories:

- [0%, 16%) under-dosing
- [16%, 35%) targeted toxicity
- [35%, 100%] excessive toxicity

Following the principle of EWOC, after each cohort of patients the dose combination recommended by the BLRM is the one with the highest posterior probability of DLT in the target interval [16%, 35%) among the doses fulfilling the overdose criterion that there is less than 25% chance of excessive toxicity.

In addition, the maximum inter-cohort combined dose escalation across the 2 combination partners is limited to 100%, where 100% refers to the sum of the relative escalation for each of the combination partners, e.g. 100% and 0% increase for LGX818 and MEK162 respectively, 0% and 100% increase for LGX818 and MEK162 respectively, etc.

Summaries of the posterior distribution of model parameters and posterior distribution of DLT rates based on the DLT data from all patients enrolled in the study and included in the DDS will be produced.

10.4.2.2 Phase II

Efficacy will be assessed using the local CT/MRI assessments evaluated under RECIST version 1.1, [Appendix 1](#). The Best Overall Response (BOR) for each patient and individual lesion measurements will be listed. The (BOR) is the best response recorded from the start of the treatment until disease progression. Based on patients' BOR during study, the Objective Response Rate (ORR) and the Disease control Rate (DCR) are then calculated.

The ORR is defined as the proportion of patients with a best overall response of Complete Response (CR) or Partial Response (PR). The DCR is defined as CR or PR or Stable Disease (SD).

Patients who withdrew prematurely due to progression of disease without having any post-dose tumor assessment will be classified as treatment failures. Similarly, patients who died due to their disease without having any post-dose tumor assessment will be classified as treatment failures.

Arm 1 dual combination: patients with metastatic BRAF V600 mutant mCRC

A Bayesian design will be used in order to estimate the true DCR. Inferential statements will be based on the uncertainty of this quantity. For a Bayesian design it is required to specify a prior distribution for the parameter of interest, in this case DCR.

For the current study, the prior clinical assumption for a MEK inhibitor in BRAF V600 mutant mCRC at pre-specified dose-levels will be used in order to derive a minimally informative unimodal Beta prior distribution that reflects the level of uncertainty around the DCR before starting the current trial. At completion of the study, this prior distribution will be updated with all the data available in this part of the study.

Once updated, the distribution summarizes the probability that the true DCR at the dose of the LGX818 and MEK162 combination used in the Phase II lies in the following categories:

- [0, 20%) unacceptable efficacy
- [20%, 30%) limited efficacy
- [30%, 40%) moderate efficacy
- [40%, 100%] clinically relevant efficacy

If the observed DCR is equal or greater than 30% (i.e. 9 or more patients with BOR of SD, PR or CR), then this will be considered as evidence of clinically relevant anti-tumor efficacy of the LGX818 and MEK162 combination in BRAF V600 mutant mCRC. Note that for a sample size of 28, if at least 9 patients with DCR are observed, then the true DCR has posterior risk of being in the unacceptable efficacy category of less than 10% ([Section 10.8](#)). If the observed DCR is less than 20% then inactivity will be declared.

A minimally informative Beta prior distribution of the true DCR is derived as follows: **a priori** it is assumed that the true mean of the DCR equals 30%. A true DCR of 30% is the midpoint between limited and moderate efficacy and serves as a compromise between a skeptical view assuming the treatment has only limited efficacy and an optimistic view assuming the treatment has moderate efficacy.

The parameters of the minimally informative Beta prior distribution of the DCR are then derived noting that $b = 1$ and $a/(a + b) = 0.30$ i.e. $a = 0.428$ and $b = 1$

Arm 2 dual combination: patients with metastatic BRAF V600 mutant melanoma who have progressed after prior treatment with selective BRAF inhibitor

A Bayesian design will be used in order to estimate the true ORR. Inferential statements will be based on the uncertainty of this quantity. For a Bayesian design it is required to specify a prior distribution for the parameter of interest, in this case ORR:

For the current study, the prior clinical assumption for a MEK inhibitor in BRAF V600 mutant melanoma at pre-specified dose-levels will be used in order to derive a minimally informative unimodal Beta prior distribution that reflects the level of uncertainty around the ORR before starting the current trial. At completion of the study, this prior distribution will be updated with all the data available in this part of the study.

Once updated, the distribution summarizes the probability that the true ORR at the dose of the LGX818 and MEK162 combination used in the Phase II lies in the following categories:

- [0, 10%) unacceptable efficacy
- [10%,15%) limited efficacy
- [15%, 20%) moderate efficacy
- [20%, 100%] clinically relevant efficacy

If the observed ORR is equal or greater than 15% (i.e. 7 or more patients with BOR of PR or CR), then this will be considered as evidence of clinically relevant anti-tumor efficacy of the LGX818 and MEK162 combination in BRAF V600 mutant melanoma. Note that for a sample size of 41, if at least 7 responses (CR or PR) are observed, then the true ORR has posterior risk of being in the unacceptable efficacy category of less than 10% (Section 10.8). If the observed ORR is less than 10% then inactivity will be declared.

A minimally informative Beta prior distribution of the true ORR is derived as follows: **a priori** it is assumed that the true mean of the ORR equals 15%. A true ORR of 15% is the midpoint between limited and moderate efficacy and serves as a compromise between a skeptical view assuming the treatment has only limited efficacy and an optimistic view assuming the treatment has moderate efficacy.

The parameters of the minimally informative Beta prior distribution of the ORR are then derived noting that $b = 1$ and $a/(a + b) = 0.15$ i.e. $a = 0.176$ and $b = 1$

Arm 3 dual combination / Arm A triple combination: patients with metastatic BRAF V600 mutant melanoma who are naïve to prior treatment with selective BRAF inhibitor

A Bayesian design will also be used in order to estimate the true ORR in these populations. Inferential statements will be based on the uncertainty of this quantity. For a Bayesian design it is required to specify a prior distribution for the parameter of interest, in this case ORR:

For the current study, a minimally informative unimodal Beta prior distribution ([Neuenschwander et al 2008](#)) is developed for ORR. The prior distribution reflects the level of uncertainty around the ORR before starting the current trial. At completion of the study, this prior distribution will be updated with all the data available in this part of the study.

Once updated, the distribution summarizes the probability that the true ORR at the dose of the dual combination (LGX818 and MEK162) and triple combination (LGX818 and MEK162 and LEE011) used in the Phase II lies in the following categories:

- [0, 30%) unacceptable efficacy
- [30%, 40%) limited efficacy
- [40%, 50%) moderate efficacy
- [50%, 100%] clinically significant efficacy

If the observed ORR is equal to or greater than 40% (i.e. 16 or more patients with BOR of PR or CR for a sample size of 40), then this will be considered as evidence of clinically relevant anti-tumor efficacy of the dual combination (LGX818 and MEK162) or triple combination (LGX818 and MEK162 and LEE011) in BRAF V600 mutant melanoma patients who have not

been previously treated with selective BRAF inhibitor. Note that for a sample size of 40, if at least 16 responses (CR or PR) are observed, then the true ORR has posterior risk of being in the unacceptable efficacy category of less than 10% (Section 10.8). If the observed ORR is less than 30% then inactivity will be declared. A minimally informative Beta prior distribution of the true ORR is derived as follows: **a priori** it is assumed that the true mean of the ORR equals 40%. A true ORR of 40% is the midpoint between limited and moderate efficacy and serves as a compromise between a skeptical view assuming the treatment has only limited efficacy and an optimistic view assuming the treatment has moderate efficacy.

The parameters of the minimally informative Beta prior distribution of the ORR are then derived noting that $b=1$ and $a/(a+b)=0.4$ i.e. $a=0.67$ and $b=1$.

Re-assessment of the MTD/RP2D

A re-assessment of the dual-combination MTD/RP2D will be performed (using dual-combination data only) after at least 10 patients in the Phase II part (aim 1 + aim 2 + aim 3) of the study have been treated for at least one cycle. A re-assessment of the triple-combination MTD/RP2D will be performed after at least 10 patients in the Phase II part of the study have been treated with the triple combination for at least one cycle. The BLRM will be re-run to confirm that the current dose combination still satisfies the overdose criteria for the model. If this combination fails to satisfy the criteria, a change to the doses under study will be made subject to the BLRM recommendation. If different RP2Ds are used for arm 1, aim 2 and aim 3, respectively, then the above re-assessment will be done by RP2D rather than combining the arms.

Enrollment in the Phase II arms will not be interrupted due to this re-assessment of the MTD/RP2D.

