10.8 Sample size calculation

Phase Ib

Dose escalation: Cohorts of 3 to 6 evaluable patients will be enrolled in the dose escalation part including at least six patients at the MTD/RP2D level, as described in [Section 6.2.4](#).

Multiple cohorts may be sequentially enrolled to the same dose level. Additional cohorts of 1 to 6 patients may be enrolled at any dose level below the estimated MTD/RP2D for further elaboration of safety and PK parameters as required. At least 18 patients are expected to be treated in the dual-combination dose-escalation part of the study, for the model to have reasonable operating characteristics relating to its MTD recommendation (see [Appendix 5](#) for details). At least 12 patients are expected to be treated in the triple-combination dose-escalation part of the study.

Phase II

Arm 1 dual combination: Based on the prior distribution and decision rules described in [Section 10.4](#), it was explored how likely it is to wrongly declare activity given the true DCR = 20%, and how likely it is to correctly declare activity given the true DCR = 40%, when 28 patients are evaluated.

- If the true DCR = 20%, the probability to wrongly declare activity (i.e. seeing at least 9 patients with SD or better) is 9.0%.
- If the true DCR = 40%, the probability to correctly declare activity (i.e. seeing at least 9 patients with SD or better) is 85.2%.

If 9 out of 28 patients have at least SD or better, then the posterior risk of the true DCR being in the unacceptable category is 7.0%.

Note: if the interim analysis is performed, the probability to correctly declare activity if the true DCR = 40% is 82.3%.

Arm 2 dual combination: Based on the prior distribution and decision rules described in [Section 10.4](#), it was explored how likely it is to wrongly declare activity given the true ORR = 10%, and how likely it is to correctly declare activity given the true ORR = 20%, when 41 patients are evaluated:

- If the true ORR = 10%, the probability to wrongly declare activity (i.e. seeing at least 7 responses) is 11.0%.
- If the true ORR = 20%, the probability to correctly declare activity (i.e. seeing at least 7 responses) is 73.9%.

If 7 out of 41 patients have PR or CR, then the posterior risk of the true ORR being in the unacceptable category is 9.8%.

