Arm 3 dual combination / Arm A triple combination: Based on the prior distribution and decision rules described in [Section 10.4](#), it was explored how likely it is to wrongly declare activity given the true ORR = 30%, and how likely it is to correctly declare activity given the true ORR = 50%, when 40 patients are evaluated:

- If the true ORR=30%, the probability of wrongly declaring at least moderate efficacy (i.e. at least 16 responses) is 11.5%.
- If the true ORR=50%, the probability of correctly declaring at least moderate efficacy (i.e. seeing at least 16 responses) is 92.3%.

If 16 out of 40 patients have PR or CR, then the posterior risk of the true ORR being in the unacceptable category is 9.0%.

11 Ethical considerations and administrative procedures

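### The Phase II success rules conclude clinically relevant efficacy at cut-offs where the plan's own posterior gives that category 9.5% to 28.1%, and in arm 2 the percentage and count forms of the rule part company off the planned sample size

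*Protocol*

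**What the plan says.** For each Phase II arm, Section 10.4.2.2 of the protocol sets a Beta prior and four ordered categories for the true rate: unacceptable, limited, moderate and a top category. For arm 1 the top category is "40%, 100%] clinically relevant efficacy". For arm 2 it carries the same name and starts at 20%. For arms 3 and A it starts at 50% and is called clinically significant.

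The success rule for arm 1 begins "If the observed DCR is equal or greater than 30% (i.e. 9 or more patients with BOR of SD, PR or CR", and the conclusion is "then this will be considered as evidence of clinically relevant anti-tumor efficacy of the LGX818 and MEK162 combination in BRAF V600 mutant mCRC". Arm 2 has the same structure: "If the observed ORR is equal or greater than 15% (i.e. 7 or more patients with BOR of PR or CR". Arms 3 and A use an observed ORR of 40%, or 16 responses in 40, and again conclude clinically relevant efficacy.

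The only posterior condition attached to the rules is that the risk of the unacceptable category is below 10%, and it is given for the planned size only, for example "Note that for a sample size of 28, if at least 9 patients with DCR are observed". Section 10.8 supplies the figures. For arm 1 at 9/28, "then the posterior risk of the true DCR being in the unacceptable category is 7.0" (per cent). For arms 3 and A it describes the cut-off differently from Section 10.4.2.2: "the probability of wrongly declaring at least moderate efficacy (i.e. at least 16 responses) is 11.5" (per cent).

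**The concern.** In arms 1 and 2 the conclusion uses the name of the top category, and in arms 3 and A a near-synonym of it, although the trigger is the floor of the category below. Even the observed rate at the cut-off lies under the top category's lower limit: 9/28 = 32.1% against 40%, 7/41 = 17.1% against 20%, and 16/40 = 40% against 50%. A result that only just passes would be reported, under a prespecified rule, as clinically relevant, while the prespecified posterior says the rate is probably lower than that. For arms 3 and A the protocol offers two different conclusions for the same 16/40.

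The second issue is that each rule is written both as a percentage and as a count. The two agree at the planned size. The denominator is the Full Analysis Set, which is every patient given at least one dose (Section 10.1.1), and no rule says which form governs if that number differs from plan.

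**Working it through.** **Inputs.** All are from the protocol. Section 10.4.2.2 gives the categories, the cut-offs and the priors, Beta(0.428, 1), Beta(0.176, 1) and Beta(0.67, 1). Section 10.8 gives the sample sizes 28, 41 and 40 and the operating characteristics.

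**Formulas.** With r successes in n patients and prior Beta(a, 1), the posterior is Beta(a + r, 1 + n − r). The probability of declaring success at a true rate p is the exact binomial tail P(X ≥ r | n, p).

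**Step 1: reproduce the stated figures.**

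| Arm | Cut-off | Success at low rate: stated / recomputed | Success at target rate: stated / recomputed | Posterior risk of unacceptable: stated / recomputed |
|---|---|---|---|---|
| 1 | 9/28 | 9.0 / 9.00% | 85.2 / 85.15% | 7.0 / 7.00% |
| 2 | 7/41 | 11.0 / 11.02% | 73.9 / 73.90% | 9.8 / 9.78% |
| 3, A | 16/40 | 11.5 / 11.51% | 92.3 / 92.31% | 9.0 / 8.96% |

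All nine agree. The separate arm 1 figure that allows for the interim analysis is not used here.

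**Step 2: the full posterior at each cut-off.**

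| Arm | Posterior | Unacceptable | Limited | Moderate | Top |
|---|---|---|---|---|---|
| 1 | Beta(9.428, 20) | 7.0% | 35.5% | 40.0% | 17.5% |
| 2 | Beta(7.176, 35) | 9.8% | 29.7% | 32.5% | 28.1% |
| 3, A | Beta(16.67, 25) | 9.0% | 41.9% | 39.6% | 9.5% |

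In arms 3 and A the top category is about as probable as the unacceptable one. The probability of at least moderate efficacy (moderate plus top) is 57.5%, 60.5% and 49.2%.

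**Step 3: arm 2 away from 41 patients.** The percentage form needs the smallest r with r/n ≥ 15%.

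- n = 40, percentage form: 6/40 = 15.0% passes. The false-positive rate is P(X ≥ 6 | 40, 0.10) = 20.6%, and the posterior Beta(6.176, 35) puts 18.6% below 10%.
- n = 40, count form: 7 are needed. The posterior risk is 8.8%.
- n = 36 to 40: the percentage form needs 6 and the count form 7. The risk under the percentage form runs from 12.9% to 18.6%.
- n = 42 to 46: both forms need 7, and the risk runs from 10.8% to 15.5%. Here the forms agree but neither keeps the 10% limit.

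**Step 4: the other arms within five patients of plan, percentage form.** Arm 1 exceeds 10% only at n = 26 and n = 30 (10.3% each) and n = 23 (12.6%). Arms 3 and A exceed it only at n = 35 (10.5%).

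**The case against.** The best defence is that the rule is an observed rate with a cap on the unacceptable category, and that its error rates are disclosed and correct. Considering a result as evidence of something is not a claim that it is more likely than not. The rule also has an 85.2%, 73.9% or 92.3% chance of declaring success when the true rate equals the lower limit of the top category. The four-category posterior is part of the planned analysis, so the 17.5% would be visible beside the claim. The low probabilities apply at the minimum passing count: at 11/28 the top category already has 44%. All of this is true. It shows that the calculation is sound and that the fault is confined to the wording of the conclusion. It does not justify naming a category that the cut-off does not support.

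For arms 3 and A the clash of names is close but not exact, because their top category is called clinically significant. The disagreement between Sections 10.4.2.2 and 10.8 over 16/40 remains.

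On sample size, the defence is largely right. A reader might infer that the percentage form fails in every arm whenever the sample size is off plan. Step 4 shows otherwise: the effect is material in arm 2, marginal in arm 1 and almost absent in arms 3 and A. A reader might also infer that the numbers will often differ from plan, but the protocol does not say so. Patients without an assessable response stay in the denominator as failures (Section 10.4.3), and Section 7.1.4.2 foresees no replacement in Phase II. The 10% limit is stated for fixed sizes, so what is left open is which rule applies off plan; no stated guarantee is broken.

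Enrolment is closed (Section 14.10.1), so a change made now is late. It alters no decision at the planned sizes and only narrows the claim.

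**Conclusion.** The point stands as a fault in the stated conclusion for all four arms. At the minimum passing count the plan's posterior gives 17.5%, 28.1% and 9.5% to the top category, and the protocol words the 16/40 conclusion in two ways. In arm 2 there is also an unresolved rule: with 40 patients the percentage form nearly doubles both the false-positive rate (11.0% to 20.6%) and the posterior risk (9.8% to 18.6%), while the count form keeps the risk at 8.8%.

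These figures rest on the protocol's own priors and on results exactly at the cut-off; higher counts give the top category more weight. The arm 2 figures also assume that the Full Analysis Set differs from 41.

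Two stronger readings are not supported. The operating characteristics in the Step 1 table are not miscalculated. Nor does the protocol promise any minimum probability for the top category, so it cannot be faulted for missing one such as 50%.

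**What to change.** 1. In Section 10.4.2.2, define success in each arm as a posterior probability below 10% for the unacceptable category at the actual Full Analysis Set size, and delete the percentage form.
2. At the planned sizes this leaves 9/28, 7/41 and 16/40 unchanged: one response fewer gives a risk of 14.7% (8/28), about 20% (6/41) and 15.5% (15/40). Add a table of the smallest r with posterior risk below 10%. From the Beta formula above it reads: arm 1, 8 for n = 23–25, 9 for 26–29, 10 for 30–33; arm 2, 7 for 36–41, 8 for 42–46; arms 3 and A, 15 for 35–37, 16 for 38–40, 17 for 41–43, 18 for 44–45.
3. Word the conclusion as unacceptable efficacy excluded, and report the posterior probability of all four categories beside it.
4. Use the same wording in Sections 10.4.2.2 and 10.8. *At least moderate* is not a safe substitute for arms 3 and A, where it has 49.2% at the cut-off.

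No 50% threshold is needed. Requiring one for the top label would take 12/28, 9/41 and 21/40, and the chance of reaching those counts at the target rates would be 44.9%, 43.8% and 43.7%.

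The cost is some text, one small table and a more modest claim at the cut-off. Sample size and the planned operating characteristics do not change. If results are already known, the report should say that the rewording came afterwards.
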